Heart failure (HF) with preserved ejection fraction (HFpEF) affects up to 32 million people worldwide. Risk factors for HFpEF include older age, hypertension, diabetes, dyslipidemia, obesity and lung disease.^{1,2} There are few effective therapies for HFpEF.^{3,4} To address this public health need, the National Institute of Health (NIH) established the Heart Share initiative to investigate pathophysiologic mechanisms and diversity in HFpEF. Heart Share includes several observational clinical research studies. The Myocardial Mechanisms in HFpEF Study (MM-HFpEF) is a prospective, multicenter, mechanistic, observational Heart Share study. The goal of MM-HFpEF is to identify altered biological pathways regulating cardiac structure and function in patients with HFpEF. To address this goal, right ventricular (RV) septal endomyocardial tissue will be procured via three transvenous endomyocardial biopsies (EMB) obtained for research purposes in patients with HFpEF referred for clinically indicated or research right heart catheterization (RHC). A blood sample will be obtained at the time of the EMB and biobanked for future correlative assays. Data from the patient's clinical evaluation or from research tests performed as part of the Heart Share Deep Phenotyping Protocol (if the patient is participating in both) will be recorded to characterize participants. The EMB samples will be used for digital histopathology and for omics analyses performed at Core Facilities designated by the MM-HFpEF Core Laboratory (Johns Hopkins University) and the Heart Share MM-HFpEF Working Group. The first broad hypothesis is that discovery multi-omics including non-destructive quantitative digital histopathology, transcriptomics, proteomics, spatial transcriptomic profiling, and spatial proteomic profiling with appropriate bioinformatic approaches will identify novel mechanisms mediating cardiac dysfunction in HFpEF as compared to non-failing (NF) Controls and HF with reduced (HFrEF). The second broad hypothesis is that among patients with HFpEF, there is myocardial pathophysiology diversity which can be identified by clinically defined or machine learning (ML) based clustering of clinical and omics data. Analytic techniques will compare findings among patients with HFpEF with different clinical and/or myocardial histopathologic phenotypic profiles. Comparator group tissues are available from hearts harvested for organ donation but ultimately not used for transplantation (NF Controls) and at explant of failing heart in patients with HFrEF undergoing cardiac transplantation. These samples will be provided to the MM-HFpEF Core Laboratory via an established collaboration with the University of Pennsylvania Cardiac Tissue Repository. Up to 300 HFpEF patients will be enrolled over a five-year period at up to 10 sites participating in the MM-HFpEF study.

1. BACKGROUND

Heart failure (HF) with preserved ejection fraction (HFpEF) affects approximately 3.0 million people in the US and up to 32 million people worldwide. As there is an incomplete understanding of HFpEF pathophysiology, there are few effective therapies for HFpEF.^{3,4} Initially, HFpEF was viewed as a sequela of hypertensive heart disease as treatment of hypertension prevents HF.^{5,6} Subsequently, a paradigm proposed that pro-inflammatory medical conditions frequently associated with HFpEF caused coronary microvascular endothelial cell inflammation, oxidative stress and deranged nitric oxide (NO) signaling with microvascular and myocardial diastolic dysfunction.⁷ Later, this paradigm was expanded to include the potential for deranged NO signalling to lead to nitrosylation and dysfunction of key unfolded protein response (UPR) effectors causing impaired clearance of dysfunctional proteins.^{8,9} To date, this paradigm has not been translated into effective therapy for HFpEF. Most recently, the potential for pathophysiologic diversity has been proposed with unique pathophysiologic HFpEF phenotypes requiring specific therapies.¹⁰ Indeed, specific therapy for the “obese HFpEF phenotype” now exists.^{11,12} However, the number of HFpEF phenotypes with specific systemic or myocardial pathophysiologic changes and unique therapeutic needs is unclear.¹³

Most evidence supporting current pathophysiologic paradigms in HFpEF comes from cardiac imaging/hemodynamic studies in humans or studies of cardiac tissue from animal models of HFpEF. Findings in animal models may or may not predict human myocardial pathophysiology.^{14,15} In contrast to HF with reduced EF (HFrEF), patients with HFpEF do not undergo cardiac transplantation where the failing heart is explanted and can be used for pathophysiologic research. Cardiac biopsies can be obtained at cardiac surgery for severe aortic stenosis (AS) or coronary artery disease (CAD).¹⁶⁻³⁸ However, studies with myocardial samples from EMB in patients with typical HFpEF and from surgical samples in patients with AS found very different findings.^{39,40} Studies most relevant to understanding HFpEF pathophysiology are those where EMB was performed to rule out specific etiologies (i.e. inflammatory or infiltrative disease) in patients presenting with a HFpEF-like syndrome with some tissue used for research. The need for EMB to rule out infiltrative or inflammatory cardiomyopathies has now been largely eliminated with advances in cardiac magnetic resonance imaging, scintigraphy and positron emission tomography.⁴ Thus, studies of HFpEF myocardial pathophysiology now use biopsies done for research purposes.^{8,29,39-66} Most previous HFpEF EMB studies were hypothesis-driven studies of hypertrophy, fibrosis, systolic or diastolic function or single biochemical pathways. Only recently have discovery approaches using transcriptomics or metabolomics been performed in human HFpEF myocardium, both from a single center.^{49,50} There is an urgent need to confirm and extend these exciting initial findings in a multicenter study inclusive of higher numbers of HFpEF patients and (potentially) more diverse HFpEF phenotypes with expanded omics approaches.

Heart Share is a National Institute of Health (NIH) funded initiative investigating pathophysiologic diversity in HFpEF. Heart Share includes studies with novel analyses of clinical data and images from previous NIH studies of HFpEF and NF Control subjects, retrospective and prospective HFpEF registries using electronic medical record (EMR) data and patient surveys and a prospective deep phenotyping (DP) clinical study including comprehensive imaging and physiologic studies with biopsies of fat and skeletal muscle in HFpEF and NF Controls. The Heart Share MM-HFpEF study will investigate myocardial mechanisms mediating cardiac dysfunction in HFpEF.

2. STUDY HYPOTHESES AND AIMS

The long-term goal of this study is to identify novel and therapeutically relevant biological pathways regulating perturbations in cardiac structure and function broadly (vs HFrEF or NF Controls) and within different HFpEF phenotypes. The first broad hypothesis is that discovery omics approaches coupled with appropriate bioinformatics will identify novel mechanisms mediating cardiac dysfunction in HFpEF. The second broad hypothesis is that there is pathophysiologic diversity at the myocardial level in HFpEF. Such diversity may track clinical characteristics (clinical phenotyping) or require computed approaches incorporating omics data. The following Specific Aims will address these hypotheses.

Aim 1. Procure three right ventricular (RV) septal endomyocardial tissue samples via transvenous EMB in patients with HFpEF referred for clinically indicated or research right heart catheterization (RHC).

Aim 2. Characterize the clinical profile of patients with HFpEF undergoing EMB.

Aim 3. Phase 1 Myocardial Tissue Multiomics: In the first approximately 100 HFpEF subjects undergoing research RV septal EMB and in simulated RV septal EMB samples from explanted heart samples from 30 NF control (unused donor) and 30 HFrEF (transplant recipients) subjects, perform quantitative, non-destructive, digital histopathology (FFPE sample), bulkRNAseq (frozen sample 1), liquid chromatography tandem mass spectrometry proteomics using data independent analysis (DIA) (frozen sample 2) and digital spatial transcriptomic and proteomic (subset) analyses (remaining FFPE sample).

Appropriate statistical approaches will determine differentially expressed (DE) genes from the bulk RNAseq data and DE proteins between HFpEF and the two comparator groups and within clinical or ML computed HFpEF phenogroups. Bioinformatic analyses will assess biological pathways suggested by the DE genes and proteins and examine any discordant information based on RNA versus protein analysis. To address the “abundant RNA/protein” limitation to whole myocardium sampling wherein the large volume of myocyte RNA/proteins may prevent detection of RNA/protein changes in other cells or the interstitium, spatial transcriptomics and in a subset, spatial proteomics will be performed in the FFPE samples. Given the rapidly evolving technology and potential for new publications relevant to this field, these analytic approaches will be reassessed by the MM-HFpEF Core Laboratory and the MM-HFpEF Tissue Working Group prior to proceeding on the first 100 EMB.

Aim 4. Phase 2 Myocardial Tissue Multiomics: In the second 200 HFpEF subjects undergoing research EMB, sample processing techniques, appropriate controls and biologic analyses will be designed by the MM-HFpEF Core Laboratory and the Heart Share MM-HFpEF Working Group to build on findings in Aim 3, evolution in omics technology and other advances in knowledge. Phase 2 analyses will include but not be limited to, snRNA-seq, targeted metabolomics, myofilament functional assessments, further spatial transcriptomic or proteomic analyses, further HFpEF phenogroup characterization and more in-depth study of specific pathways suggested to mediate HFpEF pathophysiology based on Aim 3 findings.

Aim 5. Venous blood samples (5 ml) will be taken from the superior vena cava at the time of RHC and processed for serum (red top tubes) to undergo proteomics analysis to investigate potential novel peripheral biomarkers of unique HFpEF phenogroups defined by myocardial analyses in Aims 3 and 4.

For Aims 3-5, tissue and serum analyses will be performed at Facilities chosen by the MM-HFpEF Core Laboratory and the Heart Share MM-HFpEF Working Group.

[figure not shown]
The NF Control and HFrEF comparator groups are not included in this protocol. Ex-vivo RV EMB samples are available from hearts harvested for organ donation but ultimately not used for transplantation (NF Controls) and at explant of failing heart in patients with HFrEF undergoing cardiac transplantation. Ex-vivo RV septal biopsy samples and corresponding clinical data will be provided to MM-HFpEF Core Laboratory by the Gift-of-Life organ donor program and the University of Pennsylvania Cardiac Tissue Repository through established, NIH vetted agreements.

3. STUDY DESIGN

3.1 General Description:

Patients will be consented for research RHC (if not planned for clinical purposes; 4.1 Study Procedures - RHC) and/or research EMB. Within six months of participation, patients will have had a clinically indicated transthoracic echocardiogram, NT-proBNP level, complete blood count, basic metabolic panel and electrocardiogram and/or will have these as research studies as part of this study or the Heart Share Deep Phenotyping Protocol (section 3.4).

Patients will initially be classified as “known HFpEF” or “suspected HFpEF” per criteria below (3.2 Study Population). If the patient has known HFpEF or if the patient meets resting hemodynamic criteria ($_{REST}PCWP \geq 15$ mmHg) for HFpEF, the patient will have confirmed HFpEF and the research EMB will be performed (Figure).

If the patient has suspected HFpEF and does not meet resting hemodynamic criteria for HFpEF, the risk of HFpEF will be assessed (Figure).

If the risk of HFpEF is high as evidenced by a H2FpEF score ≥ 3 or a passive leg raise (PLR) PCWP ≥ 18 mmHg, the patient will undergo research EMB. As clinical studies indicate that these patients have impaired functional capacity and increased risk of future HF,^{67,68} they will be classified as pre-HFpEF unless clinically indicated exercise hemodynamic assessment meets criteria for HFpEF (Figure).

If the patient has low risk of HFpEF based on the H2FpEF score or the $_{PLR}PCWP$, the patient does not qualify for research EMB and is classified as “not HFpEF” unless clinically indicated exercise hemodynamic assessment meets criteria for HFpEF (rare).

The research EMB (4.2 Study Procedures – EMB) will be performed using fluoroscopic or echocardiographic guidance per operator preference. If an EMB is indicated clinically, the three research EMB will be performed after the clinical EMB (usually 3-5 biopsies, per clinician specifications) have been obtained. Before and immediately after the research EMB, transthoracic echocardiographic assessment of tricuspid valve structure and regurgitation and pericardial fluid will be performed and findings recorded, along with blood pressure and heart rate.

After the research EMB and post-EMB imaging, other clinically indicated procedures (i.e. exercise hemodynamics, drug studies for pulmonary vascular function) to further evaluate HFpEF will be performed. Patients may participate in other research protocols as long as the studies do not interfere with the study entry algorithm (figure) and the ability to perform the EMB.

After the research EMB and any other clinically indicated procedures, patients will be observed for clinical stability in the catheterization laboratory post procedural area and then discharged according to routine post-procedural practice at the participating site. At discharge and at 30 days post procedure, the clinical record will be reviewed, and a case report form completed documenting any procedural related adverse events due to research RHC or EMB.

Up to 300 patients will be enrolled over a five-year period at up to 10 sites participating in the MM-HFpEF study.

3.2 Study Population

3.2.a: Inclusion criteria: Patients with known or suspected HFpEF will be identified by electronic medical record searches, referrals from clinicians, focused screening in the clinical practice including patients scheduled for RHC to diagnose or assess severity of HFpEF, responses to posting of research opportunities or review of patient lists from previous HFpEF studies.

HFpEF criteria

1. Age ≥ 30 years.
2. Left ventricular ejection fraction $\geq 50\%$ measured by echocardiography, CMR or MUGA (measured within one year + clinical stability)
3. Definition of HFpEF: signs and/or symptoms of HF, NYHA functional class II-IV, and at least one of the following:
 - a. Elevated BNP (≥ 75 pg/ml in sinus rhythm or ≥ 225 pg/ml in atrial fibrillation/flutter) or NTproBNP (≥ 225 pg/ml in sinus rhythm or ≥ 675 in atrial fibrillation/flutter) at baseline. Choice of BNP or NTproBNP is based on availability at each clinical center.
 - b. Prior HF hospitalization (primary reason for the hospitalization is HF with elevated natriuretic peptide levels [using the thresholds listed above], requiring IV diuresis for HF, or pulmonary edema or pulmonary vascular congestion on chest radiography).
 - c. Previously documented elevated pulmonary capillary wedge pressure (PCWP) at rest (≥ 15 mmHg) or during exercise (≥ 25 mmHg for supine exercise or PCWP/cardiac output ratio ≥ 2 mmHg/L/min for upright exercise).
 - d. Elevated H₂FPEF score⁶⁹ (≥ 5) or HFA-PEFF⁷⁰ score (≥ 5).

Suspected HFpEF criteria

1. Age ≥ 30 years.
2. Left ventricular ejection fraction $\geq 50\%$ measured by echocardiography, CMR or MUGA (measured within one year + clinical stability)
3. Signs and/or symptoms of HF, NYHA functional class II-IV and all of the following:
 - a. Does not meet BNP or NT-proBNP criteria for HFpEF (above)
 - b. No prior HF hospitalization meeting HF criteria (above)
 - c. No previous hemodynamic catheterization documentation of HF (as above)

3.2.b: Exclusion criteria:

According to current guidelines,⁷¹ patients deemed at increased risk of right ventricular (RV) septal EMB complications as evidenced by any of the below will be excluded.

1. Inadequate echo or fluoroscopic images.
2. Neck anatomy unfavorable for jugular venous cannulation
3. Therapy with direct oral anticoagulants without cessation for a period (age, renal function, and agent specific) deemed adequate to normalize coagulation according to local clinical guidelines.
4. Previous or ongoing therapy with warfarin with INR ≥ 1.6 measured day before or of EMB
5. Platelet count $< 50,000/\text{ml}$
6. Active bleeding or coagulation disorder
7. Infection or fever
8. Endocarditis
9. Pregnancy
10. Intracardiac thrombus
11. RV Aneurysm
12. Clinically significant tricuspid, pulmonary or aortic valve stenosis
13. Tricuspid or pulmonary mechanical valve prosthesis
14. Left bundle branch block

A known contrast media hypersensitivity is not a contraindication as contrast is not routinely used but the presence of contrast media hypersensitivity should be noted to preclude use. For patients with an indication for anticoagulation (ie atrial fibrillation), who are treated with warfarin, bridging according to local protocols if deemed advisable by the patient's clinician.

Patients with hemodynamically significant left valve disease, pericardial disease, known hypertrophic cardiomyopathy, severe non-revascularized coronary disease, or known inflammatory (i.e. myocarditis or sarcoidosis) or infiltrative (i.e. amyloidosis) cardiac diseases or known non-group 2 pulmonary hypertension are excluded.

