3.4 Primary Study Data Collected from Review of Clinical Records and Study Procedures

3.4.a: Medical History and Physical Examination: age, sex, history of hypertension, diabetes, hyperlipidemia, coronary disease, atrial fibrillation, pacemaker, myocardial infarction, chronic kidney disease, obesity (BMI ≥ 30), collagen vascular disease, lung disease (obstructive, restrictive), previous thoracic radiation or valve disease and blood pressure, heart rate, height, weight.

3.4.b: Laboratory values: creatinine, blood urea nitrogen, NT-proBNP, Hgb, Hct, platelets, white blood cells, and INR day of or day before procedure (only if on warfarin and holding for EMB).

3.4.c: Electrocardiogram: rate, rhythm (sinus, atrial flutter or AF, ventricular pacing), QRS duration, LBBB pattern (yes/no)

3.4.d: Echocardiogram: Left atrial dimension and/or volume (method), LV end diastolic dimension and/or volume (method), LV septal and posterior wall thickness, LV ejection fraction (value/method), right ventricular size (semiquantitative) and function (semiquantitative), aortic, mitral, tricuspid and pulmonary valve function (stenosis or regurgitation grade)

3.4.e: Resting hemodynamics: HR, systemic blood pressure, RA (a,v,mean), RV (systolic, end-diastolic), PA (systolic, diastolic, mean), PCWP (a,v, mean), cardiac output method (Fick indirect, Fick direct, thermodilution), cardiac output, cardiac index, PVR, PA compliance.

3.4.f: Passive Leg Raise hemodynamics: PCWP (a,v, mean)

3.4.g: Clinically indicated exercise hemodynamics (if performed): Exercise method (arm, bike upright, bike supine, other), peak level (watts, other), and same hemodynamic measures as in 3.4.e (as available).

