3.5 Primary Safety Data Collected

3.5.a: Pre-EMB echo: Echocardiographic tricuspid regurgitation grade (semi-quantitative) and pericardial effusion (window, dimension)

3.5.b: Immediate post-EMB echo: Echocardiographic tricuspid regurgitation grade (semi-quantitative) and pericardial effusion (window, dimension), tamponade physiology (yes/no)

3.5.c: Research RHC complications: death, chest pain, hemoptysis, pneumothorax, access site bleeding or hematoma exceeding usual expected severity, new atrial fibrillation/flutter, other clinically significant arrhythmias (ventricular tachycardia requiring therapy, heart block requiring therapy), pulmonary artery perforation, new or worsening tricuspid regurgitation.

3.5.d: Research EMB complications: death, chest pain, hemoptysis, pneumothorax, access site bleeding or hematoma exceeding usual expected severity, new atrial fibrillation/flutter, other clinically significant arrhythmias (ventricular tachycardia requiring therapy, heart block requiring therapy), new or worsening tricuspid regurgitation, new pericardial effusion requiring admission or serial echocardiography without intervention, tamponade requiring percutaneous pericardiocentesis, tamponade requiring surgical pericardiocentesis with or without myocardial repair.

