4.5 Tissue Analysis

4.5.a. Background: The MM-HFpEF study seeks to use discovery multi-omics to determine if there are novel, therapeutically relevant and varied (myocardial pathophysiologic heterogeneity) mechanisms mediating myocardial dysfunction in HFpEF. Most studies of human HFpEF tissue have been hypothesis driven analyses of candidate pathways. Unbiased assessment of differences in gene expression (transcriptomics) and/or protein abundance (proteomics) coupled with bioinformatic analyses to determine the pathways indicated by gene or protein changes (“omics” analysis) or integrated gene and protein changes (multi-omics) can be used to discover novel transcriptional or translational changes mediating myocardial pathology in HFpEF.

Transcriptional changes may mediate cardiac pathology in cardiomyopathies⁷⁷ and HFpEF.^{19,49} However, in endstage cardiomyopathies, dramatic differences in phenotype were unaccompanied by differences in gene expression.⁷⁸ Further, transcriptional changes did not correlate tightly with phenotype or protein changes before and after myocardial recovery in HFrEF⁷⁹ or in hypertrophic cardiomyopathy (HCM) versus controls.⁸⁰ Recent work suggests that several myocardial pathophysiologic changes maybe be predominately or jointly controlled at the translational level^{81,82} and thus, study of the proteome may reveal novel or complementary pathophysiologic information beyond changes in gene expression.

Two studies performed transcriptomics on myocardial tissue (bulkRNAseq) using LV or RV samples from HFpEF as compared to HFrEF and/or NF Controls. Both identified 13,000 to 14,000 genes but in one study (LV surgical samples from patients undergoing surgical revascularization for coronary disease with or without evidence of HFpEF), only 743 (5%) genes were differentially expressed (DE) in HFpEF versus NF controls.¹⁹ Most (719) DE genes were down regulated. In the other study with a larger sample size, 67% of genes were DE in HFpEF (RV EMB in patients with rigorously documented HFpEF) versus NF controls and 52% of genes were DE in HFrEF vs NF Controls.⁴⁹ Up-regulated (but not down-regulated) genes in HFpEF were no longer significant after adjustment for HFpEF risk factors. Both the HFpEF transcriptomic studies used bioinformatic pathway analyses to interpret the DE gene data and demonstrate alterations consistent with various theories for the pathogenesis of HFpEF.

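### The LVEF entry rule names no governing value and ignores an earlier LVEF below 50%, so recovered HFrEF enters the HFpEF group and newly reduced LVEF can.

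*Protocol*

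**What the plan says.** Criterion 2 in Protocol section 3.2.a is the same for known and for suspected HFpEF. It asks for an LVEF of at least 50%, "measured by echocardiography, CMR or MUGA", with the time condition "measured within one year + clinical stability". Clinical stability is not defined.

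Section 3.1 sets a separate requirement for baseline tests: "Within six months of participation, patients will have had a clinically indicated transthoracic echocardiogram". As an alternative, patients "will have these as research studies as part of this study or the Heart Share Deep Phenotyping Protocol". Section 3.4.d records the LVEF value and method from the echocardiogram. The echocardiogram just before biopsy (section 3.5.a) covers tricuspid regurgitation and pericardial effusion; LVEF is not among its items.

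For known HFpEF, any one item of criterion 3 is enough, on top of symptoms or signs in NYHA class II to IV. Item 3b begins "Prior HF hospitalization (primary reason for the hospitalization is HF with elevated natriuretic peptide levels" and adds further ways of documenting the admission. It sets no time limit and no condition on the ejection fraction at that admission. Under section 3.1, a patient with known HFpEF counts as confirmed HFpEF and goes to research biopsy.

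**The concern.** Aim 3 compares about 100 HFpEF patients with 30 HFrEF and 30 non-failing hearts and looks for phenogroups within HFpEF. Ejection fraction is what separates HFpEF from HFrEF in this design, yet the entry rule looks at it at one point in time, without saying which measurement is meant and without asking about its history.

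Two kinds of patient are affected:

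- **Recovered HFrEF.** LVEF was once below 50% and is now at or above it.
- **Newly reduced LVEF.** A value within the year was at or above 50%, and a later one is below it.

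If either kind is labelled HFpEF, the HFpEF group is mixed in the very respect the study wants to contrast. The difference from HFrEF may be diluted, and a phenogroup might reflect past HFrEF rather than diversity within HFpEF. The recovered patients also could not be found afterwards, because their history is not among the listed data items.

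**Working it through.** The protocol gives no figure to reproduce here, so the check is to run the two kinds of patient through the text and then to bound the effect.

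**Step 1. Recovered HFrEF.** Take a patient of eligible age with an LVEF below 50% and a heart failure admission some years ago, now stable, in NYHA class II, with an LVEF of 55% within the past year.

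| Rule | Result |
|---|---|
| Criterion 2: at least 50% within one year, stable | met |
| Criterion 3: symptoms and class II to IV | met |
| Item 3b: prior heart failure admission, any date, any LVEF | met |
| Exclusions in 3.2.b: any for earlier reduced LVEF | none |
| Section 3.1: known HFpEF | confirmed HFpEF, biopsy performed |

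This result does not depend on the gap between one year and six months. It would be the same under a six-month rule.

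**Step 2. Newly reduced LVEF.** Take 55% eleven months ago and 45% on the echocardiogram required by 3.1. Two readings are open:

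- Any value of at least 50% within the year is enough: criterion 2 is met.
- The 45% also lies within the year and fails the threshold: criterion 2 is not met.

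The text does not choose between them. The stability condition may stop some such patients, but since it is undefined, up to 10 sites can decide differently.

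**Step 3. Can these patients be found in the data?**

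- Newly reduced: yes, if the value below 50% is the one recorded under 3.4.d.
- Recovered: no. The history items in 3.4.a contain neither prior HFrEF nor an earlier LVEF, 3.4.d asks for no earlier value, and the chart review in 3.3 and the yearly data in 4.3 cover the time after enrolment.

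**Step 4. Bound on the contrast.** For one gene or protein, let the true means be m_P (HFpEF) and m_R (HFrEF), with D = m_P − m_R. Let a share p of the labelled HFpEF group lie a fraction r of the way from m_P to m_R, with r between 0 and 1. The expected observed difference is

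(1 − p)·m_P + p·[m_P + r·(m_R − m_P)] − m_R = (1 − p·r)·D.

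The protocol gives neither p nor r. Purely as an assumed range for p:

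| Assumed p | Patients in 100 | r = 0 | r = 0.5 | r = 1 |
|---|---|---|---|---|
| 0.05 | 5 | 1.00 D | 0.975 D | 0.95 D |
| 0.10 | 10 | 1.00 D | 0.95 D | 0.90 D |

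The simple (1 − p) dilution is the column r = 1, so it is the largest loss under this model.

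**The case against.** A good deal can be said for the protocol, and several stronger readings should not be drawn from it.

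- **That a newer LVEF below 50% is overridden by an older one.** A reader might infer this, but nothing says that the older value prevails. The six-month echocardiogram is itself within one year, and the stability condition is a partial safeguard. Such a patient can be labelled HFpEF; the text does not say that he or she will be.
- **That the two time windows contradict each other.** One is an entry rule covering three imaging methods. The other is a data requirement that a research echocardiogram can satisfy. They can both hold; what is missing is the link.
- **That the protocol itself shows recovered myocardium to be like HFrEF.** Section 4.5.a says that "transcriptional changes did not correlate tightly with phenotype or protein changes before and after myocardial recovery in HFrEF". It uses this to argue for adding proteomics. It does not say what myocardium with an LVEF recovered to 50% or more resembles.
- **That a known share is affected, or that these patients would form their own cluster.** The documents support neither. The HFrEF comparators are transplant explants, and no resemblance between them and stable patients with recovered or mildly reduced LVEF is shown.

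It is also fair to say that handling recovered HFrEF separately is a design choice, that section 2 (Aim 3) has the analytic approaches reassessed before work on the first 100 biopsies, and that a sensitivity analysis may stand in a statistical analysis plan not available here. Its absence is no fault of the protocol.

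The entry route in Step 1 survives all of this, as does the missing data item. An analysis cannot set aside patients whose history was not collected.

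**Conclusion.** The point holds in limited form and is a cheap improvement rather than a serious flaw. Followed exactly, the written rules class a patient with recovered HFrEF and a prior heart failure admission as confirmed HFpEF, and the listed data would not identify that patient. For newly reduced LVEF the protocol is silent, so misclassification is possible and may vary by site.

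The size is unknown. The number of affected patients cannot be derived from the protocol, and the loss in the mean HFpEF–HFrEF difference is at most the affected share. That bound assumes that affected hearts lie between the two group means. If they do not resemble explanted HFrEF hearts at all, this contrast is not diluted. The concern for the phenogroup analysis is qualitative: a history of HFrEF could contribute to a grouping and go unrecognised.

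**What to change.** Three changes:

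1. Reconcile sections 3.1 and 3.2.a with one sentence stating that the most recent LVEF before biopsy is the one tested against the study's own 50% criterion.
2. Add to section 3.4.d the lowest known prior LVEF, with its date, taken from existing records.
3. Repeat the HFpEF–HFrEF contrast and the clustering without patients who have a known earlier LVEF below 50%, and report both results.

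The second and third changes exclude nobody on the ground of an earlier LVEF; they make the subgroup visible. The first may make a few patients ineligible. The other costs are one case report form field, which will be incomplete for patients whose older records are unavailable, and one extra sensitivity analysis. No new test or visit is needed. The field is best added before much of Phase 1 has been enrolled, although it can be completed later from charts.
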